8.2.1 Screening

Subjects will be screened over a 45 day period to determine their eligibility based on specific history, physical, laboratory and imaging evaluations as per the Schedule of Assessments. Due to scheduling of the procedures, multiple visits will likely be necessary to complete the screening process. The screening assessments are outlined in Section 8.2.1.1 below. However, a single screening visit or amended screening visit schedule may be possible as follows:

- If all screening assessments and procedures can be completed within 30 days of first dose, then a single screening visit is permissible.
- The baseline MRI must be conducted within 30 days of Day 1 dosing.
- The Investigator may repeat vital signs, ECGs and laboratory tests once to verify results as based on clinical judgment at the time of the subject screening evaluation.

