8.2.1.1 Visit 1 / Screening – (-45 days to -3 days)

Screening assessments will occur within -45 to -3 days prior to Visit 2 / Day 1.

The following procedures will be performed:

- Obtain signed Informed Consent Form.
- Measure and record vital signs and InBody Scale for weight (Section 11.3).
- Evaluate subject eligibility against study inclusion/exclusion criteria.
- Record demographics and ethnicity.
- Obtain medical history including medications.
- Alcohol use assessment (history; current consumption; AUDIT Score) (Appendix A).
- Perform single 12-lead ECG (Section 11.6).
- Draw and process blood samples for laboratory tests (Section 11.5):
 - Comprehensive metabolic panel (includes liver function tests [LFTs] as well as routine chemistry panel, glucose, CPK, magnesium)
 - Hematology (CBC)
 - Serology (HIV, HepB, HCV)
 - Coagulation (INR)
 - eGFR (CKD-EPI)
- Collect and process urine sample for laboratory tests (Section 11.5):

- Routine UA (dipstick)
- Pregnancy test (female subjects)
- Drug screen
- Perform complete physical examination including a neurological examination (Section 11.2).
- Draw blood for laboratory tests (Section 11.5):
 - PEth Test
 - Serum triglycerides concentration
 - o HbA_{1c}
 - o TSH, T4
- Record concomitant medications.
- Record any AEs.

If eligible, continue with the following screening assessments:

- Perform Fibroscan prior to MRI-PDFF to assess eligibility. (Section 10.3).
- Perform Ophthalmologic examination (Section 11.3).
- Perform MRI/MRI-PDFF (Section 10.1) with 30 days of Day 1 dosing

If eligible, schedule subject to return to for the Visit 2 / Day 1 to initiate HU6 dosing.

8.2.2 Baseline Visit 2 / Day 1

Subjects will have predose assessments at Visit 2 / Day 1 prior to administering the first dose of study drug. Subjects should present to this study visit in the fasted state (minimum 8-hour overnight fast).

The following predose procedures/assessments will be conducted on Day 1:

- Confirm eligibility against study inclusion/exclusion criteria.
- Medical history to determine if any changes have occurred since the Screening visit was performed.
- Draw and process blood samples for laboratory tests (Section 11.5):
 - Hematology (CBC)
 - Comprehensive metabolic panel (includes LFT as well as routine chemistry panel; glucose, CPK, magnesium)
 - o Glycated albumin
 - o hs-CRP

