8.2.9.1 Visit 9a / Day 61 (±1 day)

On Study Day 61 (± 1 day), the following assessments will be conducted:

Subjects should present to this study visit in the fasted state (minimum 8-hour overnight fast).

The following predose procedures/assessments will be conducted:

- Collect and Review Daily Dosing Log.
- Draw and process blood samples for laboratory tests (Section 11.5):
 - Hematology (CBC)
 - Comprehensive metabolic panel (includes LFT as well as routine chemistry panel; glucose, CPK, magnesium)
 - o HbA_{1c}
 - Glycated albumin
 - hs-CRP
 - o LDL, VLDL, HDL, FFA, total cholesterol, and triglycerides
 - \circ ApoB and Lp(a)
 - HOMA-IR includes glucose, insulin, and C-peptide
- Collect and process urine sample for laboratory tests (Section 11.5):
 - Routine UA (dipstick)
 - Pregnancy test (female subjects)
 - Drug screen
- Draw and process blood samples for PD assessments:
 - OWL metabolomics and OWL lipidomics (Section 10.4)
 - SomaScan proteomics (Section 10.5)
 - ELF assay (Section 10.6)
 - Exploratory biomarkers (Section 10.7)
- Draw and process blood sample for PK (Section 9.1).
- Perform complete physical examination including a neurological examination (Section 11.2).
- Measure and record vital signs including the InBody scale (Section 11.3).
- Perform 12-lead ECG (Section 11.6).
- Record AEs and concomitant medications.
- Administer study drug (Section 6.2.1) if the visit occurs on Day 61. For those subjects whose visit occurs on Day 62, the last dose should be taken on Day 61, with no drug administered on Day 62.

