11.5 Clinical Laboratory Tests

Refer to Section 8 for clinical laboratory blood and urine collection time points.

Refer to the Study Procedure Manual for more information about sample collection, processing, storage, and shipment.

At Screening only:

- Viral serology will include testing for the presence of hepatitis B antigen, anti-hepatitis C antibody and anti-HIV antibodies.
- TSH and Free T4.
- eGFR = CKD-EPI Creatinine Equation (NKF 2009; https://www.kidney.org/content/ckd-epicreatinine-equation-2009).

Hematology testing will include erythrocyte mean corpuscular hemoglobin concentration (MCHC), erythrocyte mean corpuscular volume (MCV), hematocrit, hemoglobin, leukocyte count, and absolute counts of lymphocytes, monocytes, neutrophils, basophils, eosinophils and platelets.

Serum chemistry analyses will include glucose, calcium, albumin, total protein, sodium, potassium, bicarbonate, chloride, magnesium, blood urea nitrogen (BUN), creatinine, alkaline phosphatase, phosphate, uric acid, lactate dehydrogenase, ALT, AST, gamma-glutamyl transferase (GGT), bilirubin (total and direct), amylase, and CPK.

• Baseline ALT and AST = while each value will be recorded, the average of screening and Day 1 predose values will be used as the baseline value in the statistical evaluation of these parameters in the exploratory analysis.

Lipid panel will include total cholesterol, HDL, LDL, VLDL, triglycerides, and FFA.

Additional tests at select time points include glycated albumin, hs-CRP, ApoB, Lp(a), and HOMA-IR (includes glucose, insulin, and C-peptide; Wallace 2004), and PEth test.

- For HOMA-IR, 3 blood samples for the 3 analytes (blood glucose, serum insulin, and C-peptide) will be drawn after a minimum of 5 minutes between each sample.
- The PEth test is a serum biomarker that can assess recent alcohol consumption. The value is dependent on both quantity of alcohol and time from consumption. This will be assessed at screening and Day 28. At the discretion of the investigator, it can be obtained at other times if there is concern for excessive alcohol consumption based on history, symptoms or laboratory evaluations (e.g. elevated liver function tests). The report lists several different assays, but this study will rely on the based on PEth 16.0/18.1 (POPEth) assay, which has been validated.

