Urinalysis will consist of dipstick evaluations, with a reflex microscopic evaluation if dipstick shows blood or protein is small (1+), moderate (2+) or large (3+). Spot urine protein and albumin to be done if urine > trace protein on 2 collections.

Urine pregnancy tests will be conducted for female subjects.

Laboratory tests may be repeated once at screening. Additional laboratory evaluation may be performed at the discretion of the investigator in the assessment of an adverse event, as medically warranted.

11.6 12-lead Electrocardiogram

Refer to Section 8 for 12-lead ECG assessment time points.

Single 12-Lead ECG measurements will be obtained after the subject has rested in a supine position for at least 10 minutes. External stimuli should be kept to a minimum. Video games, watching of TV, and talking will not be allowed during this time. A digital ECG machine will be utilized for the trial. If an ECG timepoint coincides with any blood samples, the ECGs will performed \pm 10 minutes from obtaining the blood sample at the same timepoint. In addition, whenever possible, subjects should not have a meal within 2 hours prior to an ECG being performed.

The ECGs will be measured using an ECG machine that automatically calculates the heart rate and measures PR, RR, QRS, QT, and QTcF (Fridericia correction formula). The same ECG machine should be used for the same subject throughout the study, if at all possible. ECGs should be conducted in adherence with a research unit SOP acceptable to the Sponsor.

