11.7.3 Adverse Event Follow-up

Adverse events requiring therapy must be treated with recognized standards of medical care to protect the health and well-being of the subject.

Any subject who has any AE (whether serious or non-serious) or clinically significant (in the Investigator's opinion) abnormal laboratory test values will be evaluated by the Investigator or a monitoring physician, and will be treated and followed up until the symptoms or values return to normal or acceptable levels, as judged by the Investigator and the Sponsor.

Adverse events that are unresolved at end of study or upon early withdrawal will be tracked at least weekly by site staff until resolution, for 30 days, or until the subject is lost to follow-up (defined as failure to respond to three phone messages left on separate days and one certified letter requesting follow-up).

Subjects will be instructed to inform site staff of any AEs occurring during the 30-day period after discharge or early withdrawal.

Any follow-up information available at the time of the subject's end of study will be included in the clinical study report.

Any SAE that is unexpected and related to the study drug occurring after the end of study should be forwarded to the Sponsor. These cases will be handled and submitted as expedited reports but will not be included in the clinical study report.

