Normal/near normal baseline ^a : ALT ≥8× ULN Elevated baseline ^a : ALT ≥5× baseline or ≥500 U/L (whichever occurs first)	Normal Patients with Gilbert's syndrome: No change in baseline TBL	None	Interrupt study drug. Initiate close monitoring and workup for competing etiologies. Study drug can be restarted only if another etiology is identified and liver enzymes return to baseline.
Normal/near normal baseline ^a : ALT \geq 3 ULN Elevated baseline ^a : ALT \geq 2× baseline or \geq 300 U/L (whichever occurs first)	TBL ≥2× ULN Patients with Gilbert's syndrome: Doubling of direct bilirubin or increased INR to >1.5	None d	Interrupt study drug. Initiate close monitoring and workup for competing etiologies. Study drug can be restarted only if another etiology is identified, and liver enzymes return to baseline.
Normal/near normal baseline ^a :" ALT ≥5 ULN Elevated baseline ^a : ALT ≥3× baseline or ≥300 U/L (whichever occurs first)	Normal or elevated	Severe fatigue, nausea, vomiting, right upper quadrant pain	Interrupt study drug. Initiate close monitoring and workup for competing etiologies. Study drug can be restarted only if another etiology is identified, and liver enzymes return to baseline.

ALP, alkaline phosphatase; ALT, alanine aminotransferase; AST, aspartate aminotransferase; DILI, drug-induced liver injury; INR, international normalized ratio; TBL, total bilirubin, ULN, upper limit of normal.

a. Baseline ALT is derived from an average of two pre-treatment ALT measurements at least 2 weeks apart. Elevated baseline is defined as ALT \geq 1.5×ULN. In patients with a sizable stable decrease in ALT (>50% of the baseline value) during treatment, a new baseline, corresponding to the ALT nadir, should be established on an individual basis for subsequent determination of a DILI signal.

b. The actions of close observation, monitoring, and drug interruption often overlap. Occasionally, workup is initiated after drug interruption.

For further details, please see full Consensus and Recommendation list in Regev A et al., 2019.

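### The schedule does not secure the two-week spacing of baseline ALTs that Appendix C requires, and leaves up to 38 days between scheduled on-treatment liver tests

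*Protocol*

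**What the plan says.** Protocol Section 7.4 item 6 says that raised liver tests will be handled under a published consensus on drug-induced liver injury, and points to the table in Appendix C. Footnote a to that table sets two rules about baseline:

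- Spacing: "Baseline ALT is derived from an average of two pre-treatment ALT measurements at least 2 weeks apart".
- Nadir reset: "In patients with a sizable stable decrease in ALT (>50% of the baseline value) during treatment, a new baseline", equal to the lowest ALT, is to be set individually for later injury calls.

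The schedule supplies these ALT values:

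- Before treatment: screening and Day 1 predose. Section 8.2.1.1 says "Screening assessments will occur within -45 to -3 days prior to Visit 2 / Day 1". Section 8.2.1 expects that "multiple visits will likely be necessary to complete the screening process", but allows a single visit if everything is done within 30 days of the first dose.
- On treatment: Visit 6 (Day 28 ±4) and Visit 9a (Day 61 ±1). Days 2, 7, 14, 42 and 49 have no chemistry. Days 14 and 42 do have blood draws, for glycated albumin and PK.
- After treatment: Day 73 (±2).

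Section 8.2.9.1 fixes the end of dosing for a Day 62 visit: "the last dose should be taken on Day 61, with no drug administered on Day 62". Section 11.5 gives its own ALT and AST baseline for the exploratory analysis: "the average of screening and Day 1 predose values will be used as the baseline value in the statistical evaluation". It has no spacing rule.

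**The concern.** Baseline ALT does two jobs in Appendix C. It places the subject in the normal or the elevated class (the cut is 1.5 times the upper limit of normal, ULN). In the elevated class it also sets the multiples that trigger repeat testing or drug interruption. Section 7.3 excludes only ALT or AST above 5 times ULN, so the elevated rows can apply here.

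Two ALTs taken a few days apart can both catch the same transient rise, and the two-week rule guards against that. The visit schedule does not carry the rule through. A site working from Sections 8.1 and 8.2.1.1 has no prompt to observe it.

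The second matter is how often the algorithm has a value to work on. After Day 28 the next scheduled ALT is at the end of dosing. A new, lower baseline set at Day 28 would have no scheduled test to apply to until then. What is at stake is the timing of repeat testing or drug interruption in individual subjects.

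**Working it through.** The plan states no figure on this point, so there is none to reproduce. The check is date arithmetic on the visit windows, then threshold arithmetic on the Appendix C table.

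**1. Spacing of the baseline ALTs.**
- Permitted lead times: 45 − 3 + 1 = 43 days.
- Lead times under 14 days (3 to 13): 13 − 3 + 1 = 11, and 11/43 = 26%. The other 43 − 11 = 32 comply.
- On the single-visit route (3 to 30 days before Day 1): 28 permitted days, of which the same 11 fall short.
- The optional ALT/AST repeat in Section 7.3 must fall within 7 days, so it does not secure a two-week gap.

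**2. Gaps between scheduled chemistries, now.**
- Day 1 to the latest Visit 6: 32 − 1 = 31 days.
- Earliest Visit 6 to latest Visit 9a: 62 − 24 = 38 days (61 − 24 = 37 to the last dosing day).
- If *stable* means two on-treatment values, a fall seen at Visit 6 is first confirmed from scheduled draws on Days 60 to 62. With a predose draw on Day 60, at most the doses of Days 60 and 61 remain.

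**3. Direction of the threshold effect.** Write B for baseline ALT. The three ALT levels in the table are:

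| Level | Normal class | Elevated class (B ≥ 1.5 × ULN) |
|---|---|---|
| Lower (repeat if symptoms; interrupt if bilirubin criterion met) | 3 × ULN | min(2B, 300) |
| Middle (repeat if no symptoms; interrupt if symptoms) | 5 × ULN | min(3B, 300) |
| Upper (interrupt on ALT alone) | 8 × ULN | min(5B, 500) |

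The elevated-class level equals the normal-class level at B = 3/2 = 1.5, 5/3 = 1.67 and 8/5 = 1.6 × ULN respectively. If a truly normal baseline is pushed into the elevated class, the upper level therefore falls for B between 1.5 and 1.6 × ULN and rises above that. The middle level falls between 1.5 and 1.67 and rises above that. The lower level only rises.

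The documents give no ULN. For assumed values of 30, 40 and 55 U/L the crossings (lower/upper/middle) are 45/48/50, 60/64/66.7 and 82.5/88/91.7 U/L. All lie below B = 100, where the middle and upper caps start (300/3 = 500/5 = 100).

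Illustration: assume ULN 40, true ALT 50 (normal class, levels 120/200/320), and one transient rise that covers both draws if they are close but only one if they are 14 days apart.

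| Raised value | Close draws: B and levels | Spaced draws: B and levels |
|---|---|---|
| 62 | 62: 124/186/310 | (62 + 50)/2 = 56: 120/200/320 |
| 70 | 70: 140/210/350 | (70 + 50)/2 = 60: 120/180/300 |
| 90 | 90: 180/270/450 | (90 + 50)/2 = 70: 140/210/350 |

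In the first row close draws lower two of the three levels. In the other two rows they raise all three.

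The nadir reset behaves in the same way at ULN 40. A fall from 90 to 40 (50/90 = 56%) moves 180/270/450 to 120/200/320, lower throughout. A fall from 62 to 30 (32/62 = 52%) moves 124/186/310 to 120/200/320, so two levels rise.

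**4. Gaps with liver tests added on Day 14 (13 to 15) and Day 42 (38 to 46).**
- 15 − 1 = 14; 32 − 13 = 19; 46 − 24 = 22; 62 − 38 = 24. The longest is 24 days (61 − 38 = 23 to the last dosing day).
- A fall seen on Day 14 and confirmed by Day 32 leaves 61 − 32 = 29 dosing days. One seen on Day 28 and confirmed by Day 46 leaves 61 − 46 = 15.

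**The case against.** The case for leaving the plan alone has several parts.

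*Footnote a is already in the protocol.* It binds sites, and 32 of 43 permitted days satisfy it. Section 8.2.1.1 lists chemistry ahead of the Fibroscan, eye examination and MRI, so it will tend to be drawn early. This stands. A reader might infer that 26% of subjects would have a non-compliant baseline, but the 26% counts calendar days and the documents give no distribution of subjects over them.

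*Section 11.5 does not compete with Appendix C.* It averages the two values for the exploratory statistical evaluation only. This stands: the fault is a rule not carried into the schedule, and the documents do not support reading it as two conflicting definitions.

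*The harm has no fixed direction.* A reader might infer that close draws always make the algorithm less protective. The first row of the illustration shows otherwise, and the illustration assumes how the transient rise behaves. This stands.

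*The nadir reset is a matter of judgment.* Footnote a gives no number of values for *stable* and leaves the reset to the individual case, so the documents do not show that a reset is impossible before dosing ends. The full consensus, which might say more, is not reproduced. This stands. Even if one value is enough, though, a reset at Day 28 has no scheduled ALT to act on until Day 60 at the earliest.

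*Other protection exists.* The 300 and 500 U/L triggers do not depend on baseline multiples. Section 8 gives unscheduled procedures for safety concerns precedence over routine ones, and Section 7.4 lets the investigator withdraw a subject for safety. Section 11.7.3 says subjects with an adverse event or a clinically significant abnormal value "will be treated and followed up until the symptoms or values return to normal or acceptable levels", and Section 11.5 adds: "Additional laboratory evaluation may be performed at the discretion of the investigator in the assessment of an adverse event". So it would be wrong to say that subjects go unmonitored between Day 28 and Day 61. But these provisions respond to a recognised problem. A silent rise between visits need not set them off, and a falling ALT would not ordinarily do so.

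**Conclusion.** The point holds as a minor patient-safety improvement. The schedule allows a baseline that footnote a does not (11 of 43 permitted days), and it leaves up to 38 days between scheduled on-treatment liver tests, during which the adopted algorithm has only unscheduled values to use. Both statements follow from the visit windows alone.

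The size of the consequence is not known. How many subjects would be screened late, have a transient rise, or have a fall of more than half is not in the documents. The threshold examples rest on an assumed ULN and an assumed pattern of transient rise. The statement that a reset cannot be confirmed from scheduled draws until dosing is ending rests on reading *stable* as at least two values. The primary endpoint, which is measured by MRI-PDFF, is not affected.

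**What to change.** (a) In Sections 8.1 and 8.2.1.1, require the screening ALT used for the Appendix C baseline to be drawn at least 14 days before the Day 1 predose sample. The minimum lead time goes from 3 to 14 days, so the cost is at most 14 − 3 = 11 days' delay for a subject, inside the existing 45-day window. The single-visit route stays open, with 30 − 14 + 1 = 17 permitted days.

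(b) Add ALT, AST, and total and direct bilirubin to the blood already drawn on Day 14 and Day 42. This cuts the longest gap between scheduled liver tests from 38 to 24 days. It costs a few analytes at two existing draws, with no new visit.

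Both changes can go into one amendment.

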1 LIST OF ABBREVIATIONS AND DEFINITIONS OF TERMS

Abbreviation or Term	Definition
AE	adverse event
ANCOVA	analysis of covariance
BMI	body mass index
CAP	controlled attenuation parameter
CI	confidence interval
C_{max}	maximum plasma drug concentration
DNP	2,4-dinitrophenol
ECG	electrocardiogram
ELF	enhanced liver fibrosis
FAS	full analysis set
FFA	free fatty acid
HbA_{1c}	glycosylated hemoglobin (hemoglobin A1c)
HDL	high- density lipoprotein
HOMA-IR	homeostatic model assessment for insulin resistance
hs-CRP	high sensitivity C-reactive protein
ITT	intent-to-treat
LDL	low-density lipoprotein
LS Means	least squares means
MedDRA	Medical Dictionary for Regulatory Activities
MMRM	mixed model for repeated measures
MRI	magnetic resonance imaging
MRI-PDFF	magnetic resonance imaging proton density fat fraction
OWL	One Way Liver
PD	pharmacodynamic(s)
PK	pharmacokinetic(s)
POPEth	phosphatidylethanol (PEth) 16.0/18.1
QD	once daily
TEAE	treatment-emergent adverse event
VCTE	vibration-controlled transient elastography

[figure not shown]
2 STUDY OVERVIEW

This is a Phase 2a, multi-site, randomized, parallel-group, placebo-controlled, double-blind, repeated-dose study to evaluate the safety and efficacy of three oral dose levels of HU6 compared to placebo over the course of 61 days in subjects with high body mass index (BMI) and evidence of elevated liver fat.

Subjects will be screened over a 45-day period to determine eligibility based on specific history, physical, laboratory and imaging evaluations. Due to scheduling of the procedures, multiple visits will likely be necessary to complete the screening process. However, if all screening assessments and procedures, including the magnetic resonance imaging (MRI), can be completed within 30 days of the first dose, then a single screening visit is permissible.

Once qualified, subjects will be randomly assigned to one of the HU6 treatment groups or the matched placebo control group and dosed once daily (QD) in a fasting state for a total of 61 days. Subjects will return to the clinic for frequent assessment visits during the 61 days of dosing. A follow-up visit will occur within 10 to 14 days following the completion of dosing (Figure 1).

Figure 1: Study Schematic

10 Visits, Screening, Baseline/First dose, Day 2, Day 7, Day 14, Day 28, Day 42, Day 49, Day 61 / end of treatment, and Follow up at Day 71 – 75.

Visit procedures include PK and PD measures and safety assessments.

Subjects will be instructed to maintain their same diet and activity/exercise level throughout the study as they had prior to participation in the study.

Dosing will take place once daily in a fasted state. Eligible subjects will be randomized equally (N = 20 per group) to 1 of 4 treatment groups:

- Group 1: matched placebo orally once daily for 61 days.
- Group 2: 150 mg HU6 orally once daily for 61 days.
- Group 3: 300 mg HU6 orally once daily for 61 days.
- Group 4: 450 mg HU6 orally once daily for 61 days.

The randomization will be blocked and stratified by HbA_{1c} . Subjects will be stratified into two HbA_{1c} strata: one subgroup of subjects with normal baseline HbA_{1c} defined as HbA_{1c} <5.7% and the other subgroup of subjects with high baseline HbA_{1c} defined as HbA_{1c} between 5.7% and 9.0% inclusive).

